We conducted a longitudinal sensitivity analysis using all waves of data (baseline, 6-months, 12-months, 3-years) without response weights, adjusting for baseline covariates as in the primary analysis. We specified a spline model, with a linear segment between baseline and the first follow-up for initial improvement and another linear segment for the subsequent follow-ups; the two linear segments were specified to join at the first follow-up. In analyzing continuously scaled PCS-12 as the dependent variable, we used a 3-level, mixed-effects regression model by using SAS PROC MIXED. To account for the intraclass correlation due to the multilevel structure, we specified random effects at the program level and a spatial power covariance

structure at the client level to account for unequal spacing of waves. Initial explorations of 3-level, random-effects logistic models using SAS PROC GLIMMIX for binary outcomes yielded unstable estimates for program-specific random effects. We utilized a generalized estimating equation (GEE) framework with logistic regression models for binary outcomes and Poisson models for counts using SAS PROC GENMOD, specifying exchangeable correlation at the program level. From the estimated spline models, we developed a contrast involving a linear combination of coefficients to test intervention effects at each end point (baseline, 6-months, 12-months, and 3-years) and tested differences between intervention groups in change from baseline to 6 months, 12 months, and 3 years.

Exploratory analyses. The CPIC study had 2 primary outcomes: poor MHRQL (12-item mental health composite score, MCS-12 \leq 40), and depressive symptoms (PHQ-8 \geq 10 or PHQ-2 $<$ 3 for 4-year follow-up); and a community-prioritized outcome of mental wellness (a response of at least “a good bit of the time” in the previous 4 weeks to feeling calm or peaceful, having energy, or being happy), based on community input matched to the 36-item short-form health survey quality-of-life items. We developed 2 indicators: “clinical remission” (PHQ-8 $<$ 10 or PHQ-2 $<$ 3) and, with stakeholder input, “community-defined remission” (PHQ-8 $<$ 10 or PHQ-2 $<$ 3 or MCS-12 $>$ 40 or any mental wellness). We also used a count of survey periods in remission from baseline up to 3-year follow-up. Intervention status was the client’s program assignment at enrollment to CEP or RS.

For time (survey period) to first remission, we used Cox proportional hazard models for the full sample with any survey data (n = 1018), limited to those at risk for subsequent clinical (n = 995) and community-defined (n = 408) remission at baseline. We used linear regression for number of periods in remission during the course of 3 years for the full sample (n = 1018). We developed models including intervention status, adding social determinants, then depression treatment.⁵

Analyses for 4-year outcome:

We conducted intent-to-treat analyses with intervention status as the main independent variable, using logistic regression for probability of remission (clinical, community-defined) for the sample with 4-year data (n = 298). We conducted analyses parallel to the 3-year analyses noted previously, using the same covariates plus base-line measure of the outcome and the 1 baseline item differing by intervention status among 4-year completers.⁵

A5. References

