With further 20% expansion, final	780	0.20-0.22	9.98-10.92%

†Detectable effect size (mean difference between two groups divided by the standard deviation)¹⁷⁸. §Detectable percentage point difference for two groups.

6. CPIC 3-Year extension (PCORI award # 1845)

Background: Depression is a leading cause of morbidity with disparities in care. Depression collaborative care, a team-based approach supporting care management, patient activation and evidence-based treatments, is effective relative to usual care but often unavailable in under-resourced communities. Community Partners in Care (CPIC) randomized 95 programs in healthcare and community-based (e.g., social services, faith-based) service sectors in two communities to Resources for Services (RS) for individual program technical assistance versus

Community Engagement and Planning (CEP) for multi-sector coalition support for depression collaborative care. For depressed clients, CEP relative to RS reduced having poor mental health-related quality of life (MHRQL) and behavioral health hospitalization over 6-12 months. Longer-term outcomes are unknown.

Aims: This extension study of CPIC aims to:

1. Compare CEP and RS effects at 3-year follow-up, 2-years after intervention support, on primary (depression and MHRQL), community-prioritized outcomes of physical health-related quality of life (PHRQL) and behavioral health hospitalization, and outpatient services use (secondary);
2. Compare effects of CEP and RS at 6, 12, and 36 months for CPIC participants enrolled in healthcare or community-based service sectors;
3. Describe outcome priorities for African American and Latino depressed clients, and as perceived by providers.
4. Describe views of stakeholders planning the Los Angeles County Health Neighborhood Initiative (HNI) informed by CPIC; and national stakeholders briefed on CPIC and HNI.

We hypothesized that CEP relative to RS would improve long-term mental and physical health and reduce hospitalization nights, overall and within sector. We expected stakeholders to prioritize social factors and mental health.

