Methods: Extension Study (Aims 1-3): Between 1/2014-10/2014, we approached 1004 CPIC clients initially screened as depressed from 89 programs and eligible for 3-year surveys; 600 participated (60%; RS 293, CEP 307). Aim 3: For client qualitative interviews, we approached 163 consecutive 3-year survey participants stratified by depression, race/ethnicity, gender and intervention; 104 participated (64%). For staff, we notified 289 completing 12 month surveys and used purposive follow-up stratified by community, service sector and intervention, to complete 51 interviews. Aim 4: We interviewed 49 county and community leaders planning HNI and 14 of 34 leaders attending a national briefing.

Data Sources: Self-report surveys (Aims 1 and 2) and semi-structured interviews (Aims 3 and 4).

Measures: Client outcomes are poor MHRQL ($MCS-12 \leq 40$) and depression ($PHQ-8 \geq 10$) (primary); PHRQL (12-item physical composite score (PCS-12), mental wellness, and behavioral-health hospitalization nights (community-prioritized); and use of outpatient services

(secondary). Clients and providers were asked about priorities for care and national stakeholders for responses to CPIC findings and related policy initiatives.

4-year follow-up of the 3-year sample (extension study).

The CPIC 4-year follow-up was added based on *community-stakeholder input that additional follow-up of the 3-year sample was desired to show longer-term effects on depression remission*. This follow-up built on the 3-year extension study as well as an opportunity to explore of using an existing funded cohort to recruit potential subjects into the Community and Patient Partnered Research Network (CPPRN).

Analyses plan: We will conduct 3-year end-status intent-to-treat analyses, and for 4-year follow-up of the 3-year sample, 4-year end status, with intervention status as the main independent variable, adjusted for baseline status and covariates, with response weights and multiple imputation (Aim 1); subanalyses of intervention effects within service sector at each follow-up (Aim 2); sensitivity analyses (raw data, longitudinal modeling and sector-by-intervention interactions); and thematic analyses of qualitative data (Aims 3 and 4)

7. Limitations

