Appendix A

This report provides information on detailed technical methods for handling of issues for the analysis of 6-month client data as well as 12-month and 3 years follow-ups.

Table of Contents		Page
A1	Analytic Sample	A-2
A2	Weighting	A-3
A3	Multiple Imputation	A-4
A4	Analyses	A-6
A5	References for Appendix	A-10

A1. Analytic Sample

Enrollment

The study settings were South Los Angeles and Hollywood-Metro. Participant sampling (program and client recruitment) and randomization are described in greater detail in prior publications. Within enrolled programs, clients were screened for eligibility in waiting rooms (consecutive selection) or events (random selection) between March 2010 to November 2010 by community members blinded to intervention condition and supervised by RAND. Staff approached 4,645 adults (age \geq 18) over 2-3 days per program; 4440 (96%) agreed to screening. Study eligibility was limited to clients providing contact information and depressed based on a score of 10 or greater on a modified 8-item Patient Health Questionnaire (PHQ-8) (3). Of 4,440 screened, 1,322 (30%) were eligible and 1246 (94%) consented. In our previous publications,(1-3) we created enrollment weights based on propensity weighting adjustment, by fitting logistic regression models to predict the enrollment among those eligible. The reciprocal of the predicted response probability was used as the enrollment weight for each participant. See Supplementary Materials in publications. ¹⁻⁵

Telephone survey

Baseline survey. Between April 27, 2010-January 2, 2011, we approached 1,246 consented clients for baseline telephone survey conducted by survey staff blinded to intervention condition and 981 clients (79% of 1246 consented, RS: 492, CEP: 489) completed the baseline, 36 refused (RS: 17, CEP: 19), 227 were unable to contact (RS: 96, CEP: 131), and 2 deceased (RS: 1, CEP: 1).

6 month follow-up survey. Between November 2, 2010 and August 11, 2011, we approached 1093 participants (RS: 540, CEP: 553) for 6-month follow-up telephone survey; 153 enrolled participants were excluded from the contact list because their baseline survey response status was in one of following categories: final refusal, ill or incarceration, unable to contact, or deceased. Of 1093 attempted for 6-month follow-up, N=759 (69% of attempted, RS: 380, CEP: 359) completed the survey, 12 refused (RS: 3, CEP: 9), 321 were unable to contact (RS: 157, CEP: 164), and 3 deceased (RS: 1, CEP: 2).

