12 month follow-up survey. Between May 10, 2011 and March 12, 2012, we approached 974 participants for 12-month follow-up telephone survey; 272 enrolled participants were not attempted for 12-month follow-up based on their baseline or 6 month survey status. Of 974

attempted for 12-month follow-up, N=733 (75% of attempted, RS: 364, CEP: 369) completed the survey, 7 refused (RS: 4, CEP: 3), 229 were unable to contact (RS: 109, CEP: 120), and 5 deceased (RS: 3, CEP: 2).

3 year follow-up survey (extension study). Between 1/14/2014 and 10/14/2014, we attempted to contact 1004 participants for 36-month follow-up with exclusion who deceased (RS: 4, CEP: 4), who made final refusal in previous wave (RS: 22; CEP: 27), or who had no data on baseline, 6, and 12 months (RS: 84; CEP: 101). Of 1014 attempted for 36-month follow-up, 600 (600/1014=59%) participated (RS 293, CEP:307), 24 were deceased (RS:14, CEP:11), 10 refused (RS:7, CEP:3), 3 were too ill/incapable (RS:2, CEP:1), and 367 (RE:180, CEP:186) were not able to be reached.

4-year follow-up of the 3-year sample (extension study). The CPIC 4-year study was added to explore longer-term outcomes for the sample completing the 3-year follow-up, based on community stakeholder interest. In addition, this follow-up offered CPIC participants the opportunity to be participants in an additional project, the Community and Patient Partnered Research Network (CPPRN). Between 3/31/2016 and 5/26/2016, we attempted to contact 598 clients (RS: 292, CEP: 306) who completed CPIC 3 years interview participants excluding 2 that declined follow-up (RS 1, CEP 1). The telephone interview took about 15-20 minutes. At the end of the interview, a respondent was asked “Would you like to hear about the CPPRN program?” and “do you agree to be part of the CPPRN?” if answered ‘yes’. Of those, 283 (47.3%) participated (RS 143, CEP 140), with 308 not reached (RS 143, CEP 165), 1 deceased (RS 1, CEP 0), 5 refused (RS 5, CEP 0), and 1 too ill to participate (RS 0, CEP 1).⁵

A2. Weighting

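### By the appendix's fieldwork dates, the 4-year survey took place about 5.2 to 6.1 years after baseline, and the 3-year label is only approximate

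*Combined protocol and SAP*

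**What the plan says.** Section 6 (3-year extension) sets the first long-term aim as: "Compare CEP and RS effects at 3-year follow-up, 2-years after intervention support". CEP is the community engagement arm and RS the technical assistance arm. The analysis plan in the same section adds, "for 4-year follow-up of the 3-year sample, 4-year end status". Appendix A4 describes the 3-year longitudinal contrasts as changes from baseline, so baseline is the time origin.

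Appendix A1 gives the calendar dates of each telephone wave:

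- Baseline: "Between April 27, 2010-January 2, 2011, we approached 1,246 consented clients for baseline telephone survey".
- 6 months: "Between November 2, 2010 and August 11, 2011, we approached 1093 participants".
- 12 months: "Between May 10, 2011 and March 12, 2012, we approached 974 participants for 12-month follow-up telephone survey".
- 3 years: "Between 1/14/2014 and 10/14/2014, we attempted to contact 1004 participants for 36-month follow-up".
- 4 years: "Between 3/31/2016 and 5/26/2016, we attempted to contact 598 clients".

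Screening took place "between March 2010 to November 2010 by community members blinded to intervention condition". The documents give no visit windows, no observed elapsed times, and no other origin for the long-term labels.

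**The concern.** The extension asks how long a difference between the arms lasts in a condition that remits and relapses. The time point is therefore part of the conclusion. If a survey called 4-year was fielded more than five years after baseline, a null result would be read as an effect gone by year 4, when year 4 was never observed. A positive result would understate how long the effect had lasted. A reader would also take the two long-term surveys to be one year apart. Subtracting the dates in A1 suggests that neither reading is safe.

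**Working it through.** **Inputs.** All are from Appendix A1. The 3-year window is repeated, as months only, in section 6.

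| Wave | Opens | Closes |
|---|---|---|
| Baseline | 27 Apr 2010 | 2 Jan 2011 |
| 6-month | 2 Nov 2010 | 11 Aug 2011 |
| 12-month | 10 May 2011 | 12 Mar 2012 |
| 3-year | 14 Jan 2014 | 14 Oct 2014 |
| 4-year | 31 Mar 2016 | 26 May 2016 |

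**Formulas** (30.4375 days per month). Shortest possible gap = follow-up opens − baseline closes. Longest possible gap = follow-up closes − baseline opens. Typical gap = midpoint to midpoint.

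**Control: do the early labels reproduce?** Start-to-start and midpoint gaps are 6.2 and 6.7 months for the 6-month wave, and 12.4 and 13.3 for the 12-month wave. Both fit their labels reasonably well.

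**3-year wave (label 36 months).**
- Shortest: 2 Jan 2011 to 14 Jan 2014 = 1,108 days = 36.4 months.
- Longest: 27 Apr 2010 to 14 Oct 2014 = 1,631 days = 53.6 months.
- Start-to-start 44.6, end-to-end 45.4, midpoint 45.0. Excess over the label at the midpoint: 45.0 − 36 = 9.0 months.

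**4-year wave (label 48 months).**
- Shortest: 2 Jan 2011 to 31 Mar 2016 = 1,915 days = 62.9 months (62.9/12 = 5.2 years).
- Longest: 27 Apr 2010 to 26 May 2016 = 2,221 days = 73.0 months (73.0/12 = 6.1 years).
- Excess over the label: 62.9 − 48 = 14.9 to 73.0 − 48 = 25.0 months. The shortest gap exceeds 60 months, so counting completed years does not rescue the label either.

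**Gap between the two surveys (labels imply 12 months).**
- Shortest: 14 Oct 2014 to 31 Mar 2016 = 534 days = 17.5 months.
- Longest: 14 Jan 2014 to 26 May 2016 = 863 days = 28.4 months.

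**Would another origin help?** Midpoint gaps to the 3-year and 4-year waves are:

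| Origin | To 3-year | To 4-year |
|---|---|---|
| Screening (1 Mar to 30 Nov 2010; days assumed) | 46.5 | 69.4 |
| 6-month survey | 38.2 | 61.2 |
| 12-month survey | 31.6 | 54.6 |

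The two surveys are at least 17.5 months apart for any client, so no common origin can give both 36 and 48.

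**Clients without a baseline interview.** A1 reports 981 completed baselines, and A2 reports 1,018 clients with baseline or 6-month data, so 1,018 − 981 = 37 had no baseline interview. For them the natural origin is screening. The shortest possible gap to the 4-year survey is then 64.0 months, so the label fails for them too.

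**The case against.** The dates are not concealed. A1 prints every window, section 12 dates the ethics amendment for the later contact to 29 February 2016, and the title of the cited remission report spans 2010 to 2016. That rules out a simple misprint of the year, but it does not correct the label. The rest of the case for leaving the text alone has more force. It limits what can be inferred in five ways.

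- A reader might infer that the arms are compared unfairly. The documents give one contact window for both arms, so the label alone shows no such bias. The main 3-year and 4-year analyses are endpoint regressions that adjust for baseline, and time to first remission is counted in survey periods. None of these uses months.
- A reader might infer that the longitudinal sensitivity model placed the last wave at 36 months. A4 does not give the time values. It says only that the spatial power covariance was chosen because the waves are unequally spaced, which fits nominal or actual dates.
- A reader might infer that clients within the 3-year wave differ in elapsed time by 17 months (53.6 − 36.4 = 17.2). That is a bound from contact windows and not an observed spread. The same method puts the 6-month wave at −2.0 to 15.5 months, which includes impossible values. If clients were called in baseline order, nearly all would be close to 45 months.
- A reader might infer that the section 6 phrase placing the survey two years after support is wrong. No calendar end date of support is given, so it cannot be tested.
- A reader might treat both labels as equally wrong. The 3-year range starts at 36.4 months, and the 45.0-month midpoint still lies within three completed years. That label is loose. Only the 4-year label is impossible.

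**Conclusion.** The point stands as an error in the stated time of measurement. It is certain for the 4-year survey: every client was 62.9 to 73.0 months from baseline, which is 14.9 to 25.0 months later than labelled. It is probable for the 3-year survey: the window midpoint is 45.0 months, about 9 months later than labelled, and a few clients could be near 36. The interval between the two surveys is 17.5 to 28.4 months instead of 12.

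This rests on the A1 dates being correct and on baseline being the origin, as A4 implies. The windows are contact periods, so 45.0 is a window midpoint and not an observed mean. The validity of the comparison between arms is not in question. What needs correcting is any statement of how long an effect lasted.

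**What to change.** In section 6, A1 and A4:

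1. Relabel the 4-year outcome as about 5 to 6 years after baseline, and mark the 3-year outcome as a nominal label.
2. For both waves, report by arm the median and range of actual months since baseline, or since screening for clients with no baseline interview. Take these from interview dates and not from window midpoints.
3. Check the statement about two years after intervention support against the actual date on which support ended.
4. In the longitudinal sensitivity model in A4, state the time values. Use each client's actual months since baseline for both the spline and the spatial power covariance.

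The cost is wording, a short descriptive table and possibly one rerun of a sensitivity model. It should need only the interview dates and no new data collection. The small downside is that results no longer match round-number labels.

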Enrollment The enrollment weight was intended to make the enrolled sample (n=1,246) representative of a specific target population.^{6,7} That target population was defined as people who were: age 18 or older, visited a participating CPIC sites during our screening window, screened positive for PHQ-8, and provided contact information. We created enrollment weights based on propensity weighting adjustment, by fitting logistic regression models to predict the enrollment among those eligible. The reciprocal of the predicted response probability was used as the enrollment weight for each participant. Five versions of the enrollment weight were created corresponding to five imputed screener data, because imputed predictors from the

screeener data were used in fitting logistic regressions. Common predictors of age, community, and type of programs were used in all models.

Attrition The analytic sample for 6 months is comprised of 1,018 participants who completed baseline, or 6-month telephone follow-up surveys. We used nonresponse weighting to address missing data for subjects who did not who did neither complete baseline nor 6 months follow-up telephone surveys. We started with a large set of independent categorical variables to be considered for a logistic regression on the outcome of response among enrolled participants. The final model included predictors that were significant ($p < 0.05$) for either intervention arm (age, gender, ethnicity, living situation, income, US born), as well as for two design variables (community and sector of the screening program). The final weights defined on the analytic sample were the product of the two adjustment factors for enrollment and nonresponse. See Supplementary Materials in publications. We applied the weights to the 36-month outcome analysis excluding 24 deceased cases (1,004 attempted - 24 deceased = 980). The weights for 3-year main analysis defined on the analytic sample were the product of the two adjustment factors for enrollment and nonresponse. See Supplementary Materials in previous publications.¹⁻³

For 4-year follow-up, we tested bivariate associations between an indicator for responding at the 4-year survey and demographic and clinical characteristics at baseline and 3 years.⁵ The weighting model to predict follow-up status from 3-year sample included screener sector, age, education, working for pay, PCS-12, poor mental health-related quality of life at baseline, and risk for homelessness at 3 years.

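### As described, the 4-year analysis labelled intent-to-treat covers only 3-year responders, and no weight or imputation is given for clients lost at the 3-year survey

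*Combined protocol and SAP*

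**What the plan says.** - **Who was approached.** Appendix A1: "we attempted to contact 598 clients (RS: 292, CEP: 306) who completed CPIC 3 years interview participants excluding 2 that declined follow-up". The outcome of that contact was "283 (47.3%) participated (RS 143, CEP 140), with 308 not reached (RS 143, CEP 165", plus one death, five refusals and one client too ill.
- **Purpose.** Appendix A1 states the restriction openly: "The CPIC 4-year study was added to explore longer-term outcomes for the sample completing the 3-year follow-up". Section 6 also calls it a follow-up of the 3-year sample.
- **Analysis.** Appendix A4: "We conducted intent-to-treat analyses with intervention status as the main independent variable, using logistic regression for probability of remission", fitted "for the sample with 4-year data (n = 298" clients.
- **4-year weight.** Appendix A2: "The weighting model to predict follow-up status from 3-year sample included screener sector", with age, education, paid work, PCS-12, baseline poor mental health-related quality of life and 3-year homelessness risk. No further factor is mentioned.
- **3-year weight, for comparison.** Appendix A2: "The weights for 3-year main analysis defined on the analytic sample were the product of the two adjustment factors for enrollment and nonresponse". It was applied to 980 people (1,004 attempted less 24 deaths).
- **Imputation.** Section 6 plans the following for this wave: "4-year end status, with intervention status as the main independent variable, adjusted for baseline status and covariates, with response weights and multiple imputation". Appendix A3 describes item-level and unit-level imputed data from the earliest waves up to 3 years and lists no 4-year data.

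**The concern.** Being a 3-year responder is a selection made after programs were randomised. If the clients who stay differ from those who leave in their depression course, and differ in different ways under CEP and RS, the remission odds ratio among stayers need not equal the one for all enrolled clients. At 3 years the plan dealt with this by imputing non-completers and weighting the result. At 4 years the described method stops at the 3-year responders. The two waves then describe different groups, and a change in the CEP effect between them mixes time with selection. Depression remission was the reason for adding the wave, so the reader needs to know which population the estimate describes.

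**Working it through.** **Step 1: reproduce the plan's own figure.** 283/598 = 47.3%, as stated. The dispositions add up: 283 + 308 + 1 + 5 + 1 = 598; RS 143 + 143 + 1 + 5 + 0 = 292; CEP 140 + 165 + 0 + 0 + 1 = 306. The 298 in Appendix A4 does not fit this account (298 − 283 = 15 unexplained).

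**Step 2: follow the sample from enrolment (Appendix A1 and A2).**
- Enrolled: 1,246.
- Not attempted at 3 years: deaths 4 + 4, refusals 22 + 27, no survey data 84 + 101, together 242. 1,246 − 242 = 1,004. (A1 also prints 1,014 as the number attempted; 1,004 is the figure that adds up.)
- In the 3-year analysis: 1,004 − 24 deaths = 980.
- Completed the 3-year survey: 600.
- Completed the 4-year survey: 283.

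Coverage of enrolled clients is 283/1,246 = 22.7% (with 298, 23.9%). Coverage of the 3-year analysis sample is 283/980 = 28.9% (with 298, 30.4%).

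**Step 3: ask which described correction covers each loss.**

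| Step | Loss | Described correction |
|---|---|---|
| 1,246 to 980 | 266, including 8 + 24 = 32 deaths | Enrolment and nonresponse factors at 3 years; not stated for 4 years |
| 980 to 600 | 380 (380/980 = 38.8%) | Unit-level imputation at 3 years; nothing described for 4 years |
| 600 to 283 | 317 (317/600 = 52.8%) | The 4-year weight model |

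The middle row does not depend on how the silence about the product is read. The 3-year weight was applied to all 980, non-completers included, so it cannot be a weight for having completed the 3-year survey. Appendix A2 describes the nonresponse factor as addressing clients with neither a baseline nor a 6-month survey. Multiplying it in would leave 980 to 600 uncovered.

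**Step 4: retention by arm.** Enrolled totals from the baseline dispositions are RS 492 + 17 + 96 + 1 = 606 and CEP 489 + 19 + 131 + 1 = 640.
- 3-year completion: RS 293/606 = 48.3%; CEP 307/640 = 48.0%.
- 4-year response among those contacted: RS 143/292 = 49.0%; CEP 140/306 = 45.8%.
- 4-year coverage of enrolled clients: RS 143/606 = 23.6%; CEP 140/640 = 21.9%.

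**Step 5: what a fuller weight would carry.** The average weight is 600/283 = 2.1 for the last step alone, 980/283 = 3.5 to represent the 3-year analysis sample, and 1,246/283 = 4.4 to represent all enrolled clients.

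**The case against.** The case on the other side has several good parts.

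- **The restriction is disclosed.** Section 6 and Appendix A1 both name the 3-year sample as the target, so a reader should not infer that it was hidden. This stands. What it leaves is an intent-to-treat label on an analysis of completers from a selected sample.
- **The missing product is inferred from silence.** Appendix A2 lists predictors of the last response step and does not say that earlier factors were dropped. Appendix A4 calls the 4-year analyses parallel to those at 3 years, and the appendix refers readers to supplements that cannot be seen here. A reader might infer that the weights cover only the last step; the documents neither say nor exclude that. The point therefore rests on the 980-to-600 gap, which remains on either reading.
- **The whole early loss is not shown to be uncorrected.** A reader might quote 646 of 1,246 (51.8%) as unaddressed. That count includes 32 known deaths and losses that earlier factors may cover.
- **No differential loss is shown.** Three-year retention is almost equal by arm. Appendix A4 adjusts for the baseline outcome, the covariates, and one baseline item that differed by arm among 4-year completers. This limits measured baseline imbalance. It does not change the population described, and equal rates do not guarantee equal composition. The plan's own response models use homelessness, substance use, employment and poor mental health.
- **Imputation may mean item-level only.** Appendix A3 says multiple-imputation inference was used throughout, so imputed covariates plus response weights might satisfy Section 6. That is possible, but the text does not say so for this wave.
- **Intent-to-treat may mean only analysed as assigned.** The 12-month text uses the term for participants with available data. That explains the wording, but the population still needs stating.
- **The wave is exploratory.** This is correct: the 6-month, 12-month and 3-year results are untouched.

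**Conclusion.** The concern holds in a bounded form. The 4-year estimate as described applies to 3-year responders, with 283 of 1,246 enrolled clients (22.7%) contributing data. The firm gap is the 380 of 980 (38.8%) who were in the 3-year analysis but did not complete that survey: at 4 years they have neither a described weight nor a described imputation.

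The direction and size of any bias are unknown, and the documents do not establish that the 4-year result is biased. The selection matters only if responders differ from non-responders in a way that alters the CEP-versus-RS contrast. The reference group is clients enrolled in randomised programs, because programs and not clients were randomised. The percentages use 283, the figure that agrees with the A1 dispositions; using 298 changes none of the conclusions.

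**What to change.** **Preferred.** Define the 4-year weight as the product of three factors: the enrolment weight; the inverse probability of 3-year response among enrolled clients not known to be deceased; and the existing weight for 4-year response given 3-year response. Model the second factor on screener variables, and on baseline variables as imputed, because 1,246 − 981 = 265 enrolled clients have no baseline survey. Report the result as the main analysis or as a sensitivity analysis beside the present one.

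**Alternative.** Keep the present weight, remove the intent-to-treat label from the 4-year paragraph of Appendix A4, and limit the conclusion to 3-year responders.

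**In either case:**
- state the complete 4-year weight, including whether the enrolment and early-nonresponse factors are in it;
- reconcile Section 6 with Appendix A3 and A4 on whether 4-year data are imputed, and at item or unit level;
- reconcile 283 in Appendix A1 with 298 in Appendix A4.

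**Cost.** One further logistic model on data already held, and some wording. The statistical price is more variable weights (an average of about 4.4 against 2.1) and a wider interval; how much wider cannot be computed from the documents. The alternative costs only wording.
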